3.2. Scientific Rationale for Study Design

At the request of the European Medicines Agency, Paediatric Committee, and as agreed upon by PTC Therapeutics (PTC), Study 048 is being conducted as part of a Paediatric Investigation Plan (PIP) as PIP Study 7.

Translarna was granted a conditional marketing authorization on 31 July 2014 for the treatment of nmDMD in ambulatory patients aged 5 years and older. On 23 July 2018, the expansion of the indication to include patients aged ≥ 2 to < 5 years old with nmDMD was approved on the basis of comparable pharmacokinetics and consistency with the known safety profile of ataluren in PTC124-GD-030-DMD (Study 030 - PIP Study 6).

Study 048 is designed to evaluate the safety, tolerability, and PK of ataluren in male children aged ≥ 6 months to < 2 years old with nmDMD.

3.3. Justification of Dose

Participants in the study will be administered ataluren 10, 10, 20 mg/kg (morning, mid-day, and evening dose, respectively), orally or via a neonatal oral syringe (NeoMed syringe). Dosing is based on body weight, a common practice in pediatric studies that reduces variability in exposure by accommodating differences in subject size across the span of ages of the subjects who will participate in the clinical study.

The schedule of drug administration was derived directly from Phase 1 PK modeling and from Phase 2 exposure information. The intent of administering 2 smaller doses at 6-hour intervals during the day and a larger dose at a 12-hour interval overnight (eg, at 7:00 AM, 1:00 PM, and 7:00 PM) is to optimally sustain target plasma concentrations while minimizing total exposures. This schedule is likely to fit well with daily patterns of living for subjects, thus enhancing compliance. As confirmation of that premise, compliance with ataluren dosing in Phase 2 and Phase 3 testing has been excellent.

In clinical studies of ataluren in nmDMD, ataluren has been studied most extensively at the 10, 10, 20 mg/kg dose level. In the Phase 2b, randomized, double-blinded, placebo-controlled study of ataluren in nmDMD (Study 007), 57 subjects received ataluren 10, 10, 20 mg/kg for 48 weeks with a favorable risk-benefit at this dose level. Ataluren has been conditionally approved at a dose of 10, 10, 20 mg/kg for the treatment of nmDMD. Based on the collective clinical experience with ataluren 10, 10, 20 mg/kg, this dose level will be evaluated in male children ≥ 6 months to < 2 years old with nmDMD.

4. STUDY POPULATION

4.1. Overview

The study will include up to 10 subjects (minimum of 6 subjects) selected according to the following inclusion and exclusion criteria.

4.2. Inclusion Criteria

1. Signed and dated informed consent document indicating that the parent(s)/caregiver(s) of the subject has been informed of all pertinent aspects of the study prior to initiation of any study-related procedures.
2. Males ≥ 6 months to <2 years of age.
3. Body weight ≥ 7.5 kg.
4. Willingness and ability of the subject's parent(s)/caregiver(s) to comply with scheduled visits, study drug administration plan, study procedures, and study restrictions.
5. Diagnosis of DMD based on an elevated serum CK and genotypic evidence of dystrophinopathy.
6. Documentation of the presence of a nonsense mutation of the dystrophin gene as determined by gene sequencing confirmed by a PTC designee is required prior to enrollment.

4.3. Exclusion Criteria

1. Subject who is participating in any drug or device clinical investigation or whose sibling is currently participating in a blinded portion of another ataluren study or received an investigational drug within 3 months prior to the Screening Visit or who anticipate participating in any other drug or device clinical investigation or receiving any other investigational drug within the duration of this study.
2. Expectation of a major surgical procedure during the study period.
3. Prior or ongoing medical condition, medical history, physical findings, or laboratory abnormality that, in the investigator's opinion, will adversely affect the safety of the subject, or will make it unlikely that the course of study drug administration or follow-up will be completed, or will impair the assessment of study results.
4. Known hypersensitivity to any of the ingredients or excipients of the study drug (polydextrose, polyethylene glycol 3350, poloxamer 407, mannitol 25C, crospovidone XL10, hydroxyethyl cellulose, vanilla, colloidal silica, or magnesium stearate).
5. Ongoing use of the following drugs:
 - a. Systemic aminoglycoside therapy and/or intravenous (IV) vancomycin.
 - b. Coumarin-based anticoagulants (eg, warfarin), phenytoin, tolbutamide, or paclitaxel.
 - c. Inducers of UGT1A9 (eg, rifampicin), or substrates of OAT1 or OAT3 (eg, ciprofloxacin, adefovir, oseltamivir, aciclovir, captopril, furosemide, bumetanide, valsartan, pravastatin, rosuvastatin, atorvastatin, pitavastatin).

4.4. Strategies for Recruitment and Retention

A minimum of 6 male subjects will be enrolled. Subjects will be recruited from dystrophinopathy populations who receive care or are referred for evaluation at the investigational site. Subjects who have siblings with nmDMD who have a history of ataluren exposure or a nmDMD treatment plan may be eligible for this study. The principal investigator or sub-investigator will discuss the possibility of participation directly with subject's parent(s)/caregiver(s) in the clinic. Participant's sibling cannot be participating in the blinded portion of another ataluren study at the time of subject's enrollment in this study.

Advertisements approved by IRBs/ECs and investigator databases may be used as recruitment procedures.

PTC will have an opportunity to review in advance and approve the content of any study recruitment materials provided to potential study subjects' parent(s) or caregiver(s).

5. STUDY INTERVENTION

5.1. Study Intervention Administration

Ataluren will be the only study medication administered in this open-label study.

Ataluren will be supplied to the investigational site(s) by PTC for appropriate distribution to the subject's parent(s)/caregiver(s).

5.1.1. Study Intervention Description

Ataluren will be provided as white to off-white granules for oral suspension.

5.1.2. Dosing and Administration

Subjects in the study will be administered ataluren 10, 10, 20 mg/kg (morning, mid-day, and evening dose, respectively), orally or via a NeoMed syringe. Dosing will be based on body weight, a common practice in pediatric studies that reduces variability in exposure by accommodating differences in subject size across the span of ages of the subjects who will participate in the clinical study. The subject's parent(s)/caregiver(s) will be provided a Study Drug Administration Record (dosing sheet) to document daily subject compliance.

5.1.2.1. *Dose and Dosing Regimen*

Dosing of ataluren will be on a milligram of drug per kilogram of subject body weight at baseline (Visit 2). A subsequent weight-based dose adjustment may be necessary over time (see Section 5.1.2.2). All subjects will receive approximately 10, 10, 20 mg/kg ataluren TID in the morning, at mid-day, and in the evening, respectively, for 24 weeks. Ataluren will be administered orally immediately after preparation.

The amount of study drug administered to each subject, any missed doses, and the reason for noncompliance will be recorded in the source documents and electronic Case Report Form (eCRF).

5.1.2.2. *Dose Adjustments and Modifications*

Because of changes in subject body weight over time, a weight-based dose adjustment may be necessary. Weight will be re-assessed at Week 12 and ataluren dosing adjusted accordingly.

5.1.2.3. *Schedule of Drug Administration*

Ataluren administration will begin at baseline (Visit 2) and continue for up to 24 weeks. As noted in [Table 1](#), three ataluren doses should be taken per day; the first dose in the morning, the second dose during the middle of the day (mid-day), and the third dose in the evening. Ideally each dose should be taken within ~30 minutes after a meal (eg, ~7:00 AM after breakfast, ~1:00 PM after lunch, and ~7:00 PM after dinner). Intervals for dosing should be ~6 hours (± 1 hour) between morning and mid-day doses, ~6 hours (± 1 hour) between mid-day and evening doses, and ~12 hours (± 1 hour) between evening doses and the morning dose on the next day. While it is realized that variations in dosing schedule may occur in the outpatient setting, the prescribed regimen (including dosing intervals and the relationship of dosing to meals) should be followed closely on the day preceding PK sample collection in the clinic.

Table 1: Suggested Daily Dosing

Dose Designation	Preceding Meal	Example Dose Times
Morning	Breakfast	~7:00 AM - 0700 hours (± 1 hour) ↑ 6 hours ↓
Mid-day	Lunch	~1:00 PM - 1300 hours (± 1 hour) ↑ 6 hours ↓
Evening	Dinner	~7:00 PM - 1900 hours (± 1 hour) ↑ 12 hours ↓
Next Day Morning		~7:00 AM - 0700 hours (± 1 hour)

5.1.2.4. Instructions for Delays in Dosing

Dosing delays will be handled as follows:

1. If there is a delay in the administration of ataluren of <3 hours after the morning or mid-day doses or <6 hours after the evening dose, the planned dose is to be taken with no changes to the subsequent dose schedules.
2. If there is a delay in the administration of ataluren of >3 hours after the morning or mid-day doses or >6 hours after the evening dose, the planned dose is not to be taken and subjects are to resume their usual dosing schedule.

5.1.2.5. Overdose Precautions

For any subject experiencing an overdose (administration of a study drug dose >4 times the highest intended total daily dose level for this protocol [ie, >160 mg/kg/day]), observation for any symptomatic side effects should be instituted, and vital signs and biochemical and hematological parameters should be followed closely (consistent with the protocol or more frequently, as needed). Appropriate supportive management to mitigate adverse effects should be initiated. Pending the acquisition of sufficient human experience with the drug, use of gastric lavage or induction of emesis is not specifically recommended nor contraindicated.

The PTC medical monitor must be contacted if an overdose occurs. Under applicable regulations, overdosing may be considered an SAE and should be reported accordingly (see Section 7.6.2 and Section 7.6.8).

5.1.2.6. Hydration

Dehydration is a condition that occurs when the body loses too much water and other fluids that it needs to work normally. Dehydration is usually caused by severe diarrhea and vomiting, but it may also be caused by not drinking enough water or other fluids, sweating too much, fever, urinating too much, or taking certain medicines. Signs and symptoms include thirst, dry mouth, headache, fatigue, dark-colored urine, urinating less than normal, sunken eyes or cheeks, dry and cool skin, dizziness, fainting, muscle cramps, rapid heartbeat, and rapid breathing. Dehydration can be severe, especially in young children and older adults. Because of the potential risk of renal dysfunction during periods of dehydration in subjects receiving study drug, it is important

to encourage study subjects to maintain adequate hydration throughout the study. Frequent sipping or drinking of water is recommended to prevent dehydration. Subjects should be adequately hydrated prior to receiving potentially nephrotoxic agents such as aminoglycosides or vancomycin, and hydration status should be carefully monitored throughout the administration of these agents. Investigators should be particularly vigilant with subjects who are experiencing nausea, vomiting, diarrhea, or fever, or who have laboratory evidence of dehydration.

During the course of the study, breastfeeding and milk formula are allowed as part of a normal alimentation regime.

5.1.3. Formulation

Ataluren is manufactured under current good manufacturing procedures conditions. The formulation includes matrix and suspending agents, surfactants, and various excipients that aid in the manufacturing process.

5.1.4. Packaging and Labeling

Ataluren granules for oral use will be packaged in aluminum foil, child-resistant sachets (packets) and supplied in dose strengths containing 125 or 250 mg of the active drug substance. Sachets and cartons will be affixed with color-coded labels to indicate dosage strength (125 mg - yellow, 250 mg - pink).

Labels will be provided in appropriate languages as required by each country in which the study is conducted. The content of the labeling will be in accordance with local regulatory specifications and requirements.

5.1.5. Study Drug Preparation and Storage

Sachets of study drug will be shipped at labeled storage conditions and stored at room temperature (15 to 30°C [59 to 86°F]). Upon receipt at the study site, study drug(s) will be stored in a safe and secure area with restricted access and stored at room temperature 15 to 30°C (59 to 86°F).

The available stability data from representative samples support the use of the drug product for 48 months when stored at room temperature. The stability of the clinical study samples or representative samples will be monitored to support the clinical study.

Ataluren Suspension in a NeoMed Oral Syringe: Ataluren, suspended in either milk or water, remains stable for up to 1 hour at ambient temperature in the NeoMed oral syringe.

Entire content of the sachets: Study drug sachets should be stored at labeled storage conditions, away from the reach of children until time of reconstitution. For administration, the powder in the sachet may be mixed with water, milk (skim, 1% fat, 2% fat, whole milk, chocolate milk, or lactose free milk), breast milk, fruit juice, or fruit punch, or in semi-solid food (yogurt, pudding, or applesauce). The number of sachets to be taken for a dose should be separated from the total number of sachets dispensed for the subject.

For subjects with body weight <10 kg, a NeoMed oral dosing syringe (12 mL) will be used to administer an aliquot of a 25 mg/mL concentration suspension in water or milk, including breast milk. Ataluren remains stable for up to 1 hour at ambient temperature in the NeoMed oral syringe.

For subjects with body weight ≥ 10 kg, the full contents of each sachet should be well-mixed with at least 30 mL (1 ounce) of liquid, or 3 tablespoons of semi-solid food. The prepared dose should be mixed well before administration. The amount of the liquid or semi-solid food can be increased based on subject preference. Please reference the dosing instructions for further information.

The constituted ataluren suspension may be kept for up to 24 hours under refrigeration or 3 hours at room temperature.

The clinic staff will instruct each subject's parent(s)/caregiver(s) on the specific number of sachets to be taken from each kit at each dose and will provide detailed oral directions regarding drug preparation. In addition, detailed written drug mixing and dosing instructions will be provided to the subject's parent(s)/caregiver(s) when drug supplies are dispensed. The clinic staff should attempt to follow-up with the parent(s)/caregiver(s) regarding the drug preparation and dosing procedures within an appropriate interval (eg, 1 week) after initiation of study treatment.

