8.5.4. Secondary Variables - PK Parameters

The PK analyses will be performed using the PK population defined above (Section 8.4). The PK parameters will be summarized and described using descriptive statistics and results placed into context with PK data from previous studies.

The following PK parameters will be derived, when appropriate and data permitting, using noncompartmental analysis methods following the morning dose at baseline (Visit 2), Week 4 (Visit 3), and EOT at Week 24 (Visit 5):

- AUC will be derived using the linear trapezoidal rule during the ascending portion of the curve and the log-trapezoidal rule during the descending portion of the curve. AUC_{0-24} after the morning dose and $AUC_{0-\tau}$ following every dose will be derived.
- C_{max}
- T_{max}
- C_{trough} (concentration prior to the morning dose)

Apparent clearance (CL/F) and $T_{1/2}$ may also be assessed, if feasible.

The PK parameters will be investigated based on frequent blood sampling. At each assessment period, blood sampling will occur at pre-dose, and 1-, 2-, 3-, and 4-hours post-dose following the morning and mid-day ataluren doses, and at pre-dose, 1-, 2-, 3-, 4-, and 12- (before the next day dose) hours after the evening ataluren dose.

Blood/plasma partitioning will be determined at 2.5 hour and 4.5 hour post morning ataluren dose at each visit.

8.5.4.1. *PK Analysis Methods*

Observed values of plasma concentrations for ataluren will be summarized at baseline (Visit 2), Week 4 (Visit 3), and EOT at Week 24 (Visit 5).

Individual PK parameters will be derived using actual sampling and dosing times. The PK parameters will be summarized with descriptive statistics at baseline (Visit 2), Week 4 (Visit 3), and EOT at Week 24 (Visit 5). (eg, n, arithmetic mean, standard deviation, standard error, median, min, and max, CV% mean, geometric mean, and CV% geometric mean). The analysis will be performed with a fully validated version of Phoenix WinNonlin V6.3 or higher.

Additional information will be provided in the PK analysis plan.

8.5.5. *Other Variables*

8.5.5.1. *Vital Signs and Physical Examination*

Vital signs (height, weight, BMI, systolic and diastolic BP, and heart rate) and physical examination data will be listed and summarized by visit and overall. Where appropriate, changes from baseline will be summarized by visit.

8.5.5.2. *Laboratory Values*

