7.3. Blood Pharmacokinetic Parameters

Blood PK parameters for ataluren will be estimated using non-compartmental methods with WinNonlin®. Any data points designated as anomalous values that would impact PK should be predefined before database lock if possible and identified in the report with a rationale for exclusion. The PK parameters will be estimated from the concentration-time profiles, and AUCs will be calculated using the Linear-Log Trapezoidal method (equivalent to the linear up / log down option in WinNonlin). For the estimation of PK parameters, BQL concentration following first dose at pre-dose and up to the first measurable concentration will be set to zero, BQL concentration will be set to missing otherwise. Actual sampling times, rather than scheduled sampling times, will be used in all computations involving sampling times. Actual dose will be used to calculate dose-dependent parameters. Parameters will be summarized by dose (morning, mid-day, evening) and entire day, and visits (baseline, Week 4, and EOT at Week 24). AUC0-tau and AUC0-inf for a subject at any specific dose interval will be reported as NR (not reportable) if there is one sample missing during the dose interval, and consequently the AUC0-24 for the subject at the specified day will be reported as NR.

The following blood PK parameters will be determined using non-compartmental methods as appropriate, for each visit:

Parameter	Description	Dose
C _{max}	Maximum blood concentration; determined directly from the concentration time profile; if the maximum blood concentration occurs at more than one time point, C _{max} is defined as the first maximum value	Morning, Mid- day, Evening
T _{max}	Time to C_{max} ; if the maximum value occurs at more than one time point, T_{max} is defined as the first time point with this value.	Morning, Mid- day, Evening
Ctrough	Trough blood concentration; measured blood concentration at the end of the dosing interval, directly before next administration.	Morning,

Parameter	Description	Dose
AUC ₀₋₂₄	Area under the blood concentration vs time curve (AUC) from time 0 to 24 hours post first morning dose.	Morning
AUC _{0-т}	AUC from time 0 to 6 hours post-dose following the morning and mid-day ataluren doses and AUC from time 0 to 12 hours post- dose following the evening ataluren doses. AUC from time 0 to 6 hours post-dose following the evening ataluren dose will also be calculated.	Morning, Mid- day, Evening

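### Whole sachets from 10 kg upward can move the mg/kg given away from the nominal dose, and SAP 7.3 reports AUC, Cmax and accumulation ratios with no version normalised to the dose given

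*Protocol*

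**What the plan says.** **Dose.** Protocol 5.1.2.1 sets the target: "All subjects will receive approximately 10, 10, 20 mg/kg ataluren TID". Protocol 3.3 and 5.1.2 justify dosing by weight on the ground that it "reduces variability in exposure by accommodating differences in subject size". Protocol 5.1.2.2 adds: "Weight will be re-assessed at Week 12 and ataluren dosing adjusted accordingly".

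**Preparation.** Sachets are "supplied in dose strengths containing 125 or 250 mg of the active drug substance" (Protocol 5.1.4). Protocol 5.1.5 gives boys under 10 kg a measured aliquot of a 25 mg/mL suspension by oral syringe. For boys of 10 kg or more, "the full contents of each sachet should be well-mixed with at least 30 mL (1 ounce) of liquid", and caregivers are told how many sachets make up each dose. The sachet counts are in dosing instructions and a dosing table that are not among the documents.

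**Analysis.** Protocol 8.5.4 plans descriptive summaries, with "results placed into context with PK data from previous studies". SAP 7.3 states: "Parameters will be summarized by dose (morning, mid-day, evening) and entire day, and visits (baseline, Week 4, and EOT at Week 24". Its parameter table includes Visit 3/Visit 2 and Visit 5/Visit 2 accumulation ratios for Cmax and AUC0-tau. It has no dose-normalised AUC or Cmax. Only CL/F and Vz/F contain the dose. For dose-dependent parameters, the text before the table says the actual dose will be used, and the text after it says the planned dose, taken from the study's dosing table.

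**The concern.** An aliquot can follow body weight closely, but a count of 125 mg units cannot. From 10 kg upward the mg/kg given therefore depends on where a boy's weight falls relative to the sachet steps. Exposure summaries that ignore this mix two things: how the drug behaves in this age group, and how far the given dose was from nominal.

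Two uses of the data are exposed. One is the reading of AUC and Cmax against earlier studies, which Protocol 1.3.1 stresses when it speaks of confirming a similar PK profile. The other is the Visit 5/Visit 2 accumulation ratio. The dose is re-set at Week 12, between the Week 4 and Week 24 profiles, so a change in mg/kg or in preparation at that point enters the ratio directly. With 6 to 10 boys, one or two such cases can move a mean.

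**Working it through.** **Inputs.** Nominal dose 10, 10, 20 mg/kg (Protocol 5.1.2.1); sachets of 125 and 250 mg (5.1.4); whole sachets from 10 kg and 25 mg/mL aliquots below (5.1.5); minimum entry weight 7.5 kg with no upper limit (4.2); dose-proportional concentrations in older boys in Study 007 (1.3.1).

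**The plan's own figure.** Protocol 5.1.2.5 defines overdose as "administration of a study drug dose >4 times the highest intended total daily dose level for this protocol [ie, >160 mg/kg/day". The nominal daily total is 10 + 10 + 20 = 40 mg/kg, and 4 × 40 = 160, so the figure reproduces.

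**Below 10 kg.** At 9.9 kg a 10 mg/kg dose is 99 mg, or 99/25 = 3.96 mL. The nominal dose can be met.

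**At 10 kg and above.** Each dose is 125k mg with k a whole number, and mg/kg = 125k/weight. Two rounding rules are shown because the dosing table is not available. Nearest-sachet takes the multiple closest to 10 × weight (morning, mid-day) and 20 × weight (evening). Round-up takes the first multiple at or above those targets. Percentages are against 40 mg/kg/day.

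| Weight (kg) | Target (mg) | Nearest (mg) | mg/kg per dose | mg/kg/day | Round-up (mg) | mg/kg/day |
|---|---|---|---|---|---|---|
| 10 | 100/100/200 | 125/125/250 | 12.5/12.5/25 | 50.0 (+25%) | 125/125/250 | 50.0 (+25%) |
| 12.5 | 125/125/250 | 125/125/250 | 10/10/20 | 40.0 (0%) | 125/125/250 | 40.0 (0%) |
| 13 | 130/130/260 | 125/125/250 | 9.6/9.6/19.2 | 38.5 (-4%) | 250/250/375 | 67.3 (+68%) |
| 15 | 150/150/300 | 125/125/250 | 8.3/8.3/16.7 | 33.3 (-17%) | 250/250/375 | 58.3 (+46%) |
| 15.6 | 156/156/312 | 125/125/250 | 8.0/8.0/16.0 | 32.1 (-20%) | 250/250/375 | 56.1 (+40%) |

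- The per-dose deviations at 10 and 15 kg need no rounding assumption, since no multiple of 125 mg is closer to any of those targets. Closest is judged dose by dose here. A rule that balanced the daily total could give another split.
- Under nearest-sachet rounding the evening dose changes at 312.5/20 = 15.6 kg and the day doses at 187.5/10 = 18.75 kg. From 10 to 15.6 kg the dose is therefore a constant 125/125/250 mg.
- 125 mg lies within 10% of the 10 mg/kg target from 125/11 = 11.4 kg to 125/9 = 13.9 kg.

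**Accumulation ratio.** Take a boy of 9.5 kg on a 95 mg aliquot at Visit 2, and 10.2 kg on a 125 mg sachet from Week 12 (assumed weights, with 10.2 kg also used at Week 24).

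- mg: 125/95 = 1.32.
- mg/kg: (125/10.2)/(95/9.5) = 12.25/10 = 1.23.
- If he weighs 10.5 kg at Week 24: (125/10.5)/10 = 1.19.

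With linear PK and constant clearance per kg, the morning AUC0-tau ratio is about 1.23 with no accumulation, and dividing by mg/kg returns it to 1.00. If clearance in L/h did not change, the observed ratio is 1.32 and the normalised one 1.32/1.23 = 1.07. The Visit 3/Visit 2 ratio precedes the Week 12 re-assessment, so that re-assessment does not affect it.

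**Whether CL/F fills the gap.** It is Dose/AUC0-inf and needs a terminal slope, which SAP 7.3 does not assign when Tmax is among the last three points. On samples at 0, 1, 2, 3 and 4 h, a Tmax of 2 h or later fails; if the next pre-dose sample at about 6 h is counted, 3 h or later fails. The choice of dose also matters. If planned dose meant nominal mg/kg × weight, CL/F at 10 kg would be 100/125 = 0.80 of its value on the amount given. If the table lists sachet amounts, the two agree when dosing is correct.

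**The case against.** The strongest reply is that the protocol promises only an approximate mg/kg, so sachet rounding is expected, and that exposure under the regimen as given is a legitimate main summary. The amount given is recorded (Protocol 5.1.2.1), weight is measured at every PK visit (7.3.5), and SAP 4.1 lists every eCRF domain by subject. With 6 to 10 boys, a reader could work out mg/kg by hand. The PK analysis plan announced in Protocol 8.5.4.1 may already include normalisation. All of this stands, and it is why the point is a low-cost improvement. It does not correct the accumulation ratios as defined, nor does it settle which dose enters CL/F.

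A reader might also infer more than the documents support:

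- **That sachets cannot deliver the dose from 10 kg upward.** At 12.5 kg they do so exactly, and from about 11.4 to 13.9 kg each dose is within 10%.
- **That dosing is in effect flat above 10 kg, so the Week 12 re-assessment does nothing there.** This needs nearest-sachet rounding and holds only to about 15.6 kg. Under round-up the dose steps at 12.5 kg.
- **That dose is confounded with age.** Preparation splits on weight, and no weight distribution is given. If weights were uniform from 10 to 15 kg (assumption), the mean would be 500 × ln(1.5)/5 = 40.5 mg/kg/day, almost the aliquot group's 40.
- **That the plan formally compares exposure with earlier studies.** The secondary objective is only to assess the PK, and earlier data serve as context. Whether those studies had similar sachet rounding is not stated; if they did, unadjusted values would be closer to like for like.

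**Conclusion.** The point holds as a gap in the PK analysis. At 10 kg and above, whole sachets put the closest achievable dose between 25% above nominal (10 kg) and 17% below (15 kg), passing through exact at 12.5 kg, and SAP 7.3 reports no AUC, Cmax or accumulation ratio normalised to the dose given. A change from aliquot to sachet at Week 12 can produce an apparent Visit 5/Visit 2 ratio of about 1.2. CL/F is not a dependable substitute, and the SAP contradicts itself on the dose behind it.

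The deviations at 10 and 15 kg follow from the sachet strengths alone. The range from 50 to 32 mg/kg/day over 10 to 15.6 kg assumes nearest-sachet rounding, and the ratio of 1.23 assumes linear PK, constant clearance per kg and the weights shown. How many boys fall at the affected weights is unknown. Confidence is moderate, because the dosing table and the PK analysis plan are not among the documents. This is a cheap improvement and does not call the design into question.

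**What to change.** In SAP 7.3 and Protocol 8.5.4:

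1. Derive and list the mg/kg given for each dose on each PK day, from the recorded amount and the weight at that visit.
2. Report AUC0-tau, AUC0-24, Cmax and the accumulation ratios also normalised to the mg/kg given, beside the observed values. Use both when setting results against earlier studies, and state the linearity assumption.
3. Flag each individual value by preparation (aliquot or whole sachet).
4. Reconcile the two statements in SAP 7.3 on actual versus planned dose.

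The sponsor should also reconcile the stated mg/kg in Protocol 3.3 and 5.1.2 with the preparation instruction in 5.1.5. No view is taken here on which dose or sachet rule is right.

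The cost is some SAP wording and a few extra table columns. Amount given and weight are already collected, so no new procedure or sample is needed. If the PK analysis plan already covers items 1 to 3, a cross-reference to it is enough for those.
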